Low-intensity versus high-intensity home-based treadmill training and walking attainment in young children with spastic diplegic cerebral palsy

NCT #: NCT02424526

Date: 7/29/2014

Study Protocol and Statistical Analysis Plan

Study Design

This is a prospective randomized controlled study which will include 24 pre-ambulatory children with CP under 3 years of age (i.e. up to the child's third birthday), GMFCS levels I and II.

Study Sites

All assessments and interventions will be conducted at the children's homes. In order to achieve a culturally and ethnically diverse sample, children will be enrolled at three sites in two US states. [name] will enroll children at the Seattle, WA site, [name] will enroll children at the Tacoma, WA site and [name] will enroll children at the Sacramento, CA site. Seattle, WA has a relatively high-income White (non-Hispanic descent) and Asian urban population; Tacoma, WA has a relatively lower-income White, Black and Hispanic urban population; Sacramento, CA has a relatively middle-income Hispanic, Black and Asian urban and rural population.²³ Conducting the study at these 3 sites will enable us to better generalize the results to a larger population.

Participants and Characteristics

24 pre-ambulatory children with CP under 3 years of age, GMFCS levels I and II, with bilateral impairment, who show signs of walking readiness will be recruited at the 3 different study sites. Eight children will be randomly assigned to a low-intensity or a high-intensity treadmill training group at each site.

Inclusion criteria will include

- Signs of walking readiness as demonstrated by the ability to sit for 30 seconds when placed and to take 5 to 7 steps when supported at the trunk or arms. These criteria were used in previous research to assure that the children had sufficient trunk control and bipedal control for the treadmill intervention.¹⁷ Children will be pre-ambulatory and will not engage in regular ambulation with an assistive device outside of physical therapy.
- Because young children often are not formally diagnosed with CP until 2 years of age, we will include children
 - who show bilateral symmetrical or asymmetrical impairment (i.e. diplegia and quadriplegia, but not hemiplegia)
 - who demonstrate upper motor neuron signs (i.e. spasticity and/or hyperreflexia)
 - who have been identified as high-risk for a motor disability by a physician

Exclusion criteria will be

- a history of uncontrolled seizures

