- StepWatch data will be collected for all awake daytime hours over a 7 day period at study onset before treadmill training commences and at each of the post-intervention assessments. The StepWatch accelerometer has been shown to reliably measure walking activity in children with CP.²⁶ To assure consistency in data collection, study investigators will participate in a 2-day training session prior to study onset. Training in use of StepWatch accelerometers and treadmills, standardization of training protocols and administration of outcome measures will assure inter-rater reliability.

Enrollment procedures

An equal number of children will be enrolled at each site for a total of 8 children per location. Of these eight children, four children will be randomly assigned to the low-intensity and four will be assigned to the high-intensity group. Randomization will be conducted via blinded drawing from administrative personnel at their respective sites.

The PI and C-PIs are all engaged in clinical practice at their facilities and have professional connections with medical and therapy facilities in their communities. At each site, advertisement for the study will be conducted via posted flyers, electronic flyers and word-of-mouth recruitment.

[name] will recruit children from Alta Regional Center Sacramento, the area's main provider of early intervention services, from Easter Seals Sacramento, from Shriners Hospital Northern California, from University of California Children's Hospital, from Sutter Hospital Sacramento, and via the Sacramento Pediatric Therapy Interest Group. [name] successfully recruited from these sources for past studies and is known for her research in the medical and therapy community. Staff support for recruitment will come from professional connections at each recruitment site and at the University.

[name] will use a directed recruitment mailing to children and their families who have received care at Seattle Children's Hospital and to community therapy providers in Western Washington State. Seattle Children's Hospital provides care to ~ 800 children with cerebral palsy each year primarily through Developmental and Rehabilitation medicine departments. [name] has an extensive history of recruitment for clinical trial for children with CP (i.e. Selective Dorsal Rhizotomy, Botox and Intrathecal Baclofen).

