[name] will recruit from local early intervention providers (including Birth to Three Developmental Services, A Step Ahead in Pierce County, and Tacoma Learning Center), Mary Bridge Children's Hospital, the Children's Therapy Unit, and from Washington Pediatric Special Interest Group. [name] has successfully recruited subjects from these sites previously.

No problems with recruitment of study participants are anticipated due to each investigator's connections in their local medical community. If one of the sites should fall short of qualified children, more children could be covered at one of the other sites. Drop-out rates are expected to be low due to the home-based nature of the study. All of the outcome measures as well as the intervention will be conducted at the children's homes. It is possible that a young child might fall sick for any of the planned visits by the PIs, or might not fully participate in one of the visits for other reasons. In this event, the PI will reschedule a repeat visit within a few days of the original visit to collect the data.

Between the three sites, twelve children will receive high-intensity treadmill training and twelve children will receive low-intensity treadmill training. Due to the stringent inclusion and exclusion criteria, the children in the two groups are expected to show no significant between-group differences at baseline. In [name] previous study on home-based treadmill training, group allocation using the same criteria led to two groups with no significant differences regarding age and developmental skills.¹⁷

Power Analysis

Power analysis was conducted to determine a sample size based on developmental data and based on StepWatch data.

To examine the optimal dosing for walking attainment, a projected sample size of 18 subjects (9 per group) at 95% power was calculated from Peabody Developmental Motor Scales-2 Locomotion subscale change scores from [name] previous home-based treadmill training study (n=12; GMFCS levels I and II; ages 15-32 months)¹⁷. An additional 6 subjects will be added to strengthen the study design and allow for possible attrition, leading to a total number of 24 subjects.

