To assure sufficient power to assess the effects of treadmill training on overall walking activity, a proposed sample size of 12 per group would have 80% power to detect a 3000 stride/day difference in treatment intensity as measured with the StepWatch monitor. This is based on [name] cross-sectional StepWatch average stride/day data from 17 youth with CP ages 2-3 years where the mean difference between GMFCS level I and II was 3000 strides.¹⁸

[figure not shown]

Fig. 4. Power analysis for sample size ($\alpha = 0.0$; Power= 0.95; Effect size=1.87; Sample size=18)

Methodology

Approval from the University Institutional Review Board was submitted on July 10, 2014 and approved on July 29, 2014 by the lead institution at California State University, Sacramento. A cooperative agreement will be put in place prior to study onset with the other institutions (please see attached). Due to the children's young age, written informed consent will be obtained from the parents. Parents will be asked to commit to a 6-week stretch uninterrupted by vacations or breaks. Study participation will be discussed and scheduled carefully with the families to allow for 6 weeks of uninterrupted intervention period. Due to the nature of the home-based administration of the intervention by parents and caregivers, high adherence to the study protocol is expected. Investigators will schedule weekly home visits and all assessments at a mutually agreed upon time that is convenient for the families.

After consenting to study participation, the parents for each child will fill out a parent questionnaire containing demographic and health information about their child. A physician form will also be signed prior to study onset to seek medical clearance for the child for the intervention. Group allocation will be determined by blinded drawing from a hat until each of the three study sites has reached a total of 4 children in each group. In the unlikely event that one site might have difficulty with subject recruitment, additional children will be enrolled at another study site.

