A one-way analysis of variance (ANOVA) with repeated measures will be used for comparison of treatment groups for parametric dependent variables, i.e. PDMS-2, GMFM, Timed 10-meter Walk Test, and 1-minute Walk Test. Analysis for non-parametric data for dependent variables, i.e. PEDI and FMS, will be conducted using the Friedman test for comparison between groups. StepWatch data will be examined with the Wilcoxon sign rank test for paired data. Post hoc tests will be performed where appropriate. Alpha will be set at 0.05. In addition, data on whether children reached the minimum clinically important change will be reported for the GMFM.³⁷

[figure not shown]
Study Timeline

Overall Study Timeline

Study recruitment will commence as soon as all study sites have signed the cooperative IRB agreement. All equipment will be ordered immediately after the receipt of the grant. Training on StepWatch use will be conducted by [name] at Seattle Children's Research Institute. [name] and [name] will participate. During the same meeting, reliability training will be conducted on other outcome measures. Recruitment and enrollment will commence immediately by distributing study information at the three sites. It is anticipated that there will be coinciding intervention and data collection for the 8 children at each site for the duration of 15 months. Two treadmills will be available at each site for the 6-week treadmill intervention periods for each child. Video review will be ongoing by the consultant, who is blinded to group allocation, as the videos become available for each child. Preliminary data analysis will be conducted in order to present initial results at conference within the grant period. Once all data is collected, there will be a second on-site meeting of the three PIs in order to assure consistent data entry and to allocate the responsibilities for study result dissemination. All three investigators will engage in manuscript preparation with [name] as first author. Data analysis will be performed by a statistician at the lead institution in collaboration with the PIs. Manuscript preparation will be conducted in the final two months of the 24-month study period.

Study Timeline for Each Subject

As indicated above, each child will be enrolled in the study for a total period of 26 weeks.

Human Subjects

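### The draw is balanced 4:4 within three sites, but the between-arm ANOVA has no site term: a small, conservative loss of efficiency that is cheap to avoid

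*Combined protocol and SAP*

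**What the plan says.** Study Sites explains that the three sites were chosen for their different populations: "In order to achieve a culturally and ethnically diverse sample, children will be enrolled at three sites in two US states". A different investigator enrols at each. Under Interventions, the investigators make the weekly home visits, adjust treadmill speed and correct the parents' technique.

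Enrollment procedures restricts allocation by site: "Of these eight children, four children will be randomly assigned to the low-intensity and four will be assigned to the high-intensity group". Methodology describes the mechanism as "blinded drawing from a hat until each of the three study sites has reached a total of 4 children in each group". Both sections allow an exception. Enrollment procedures says "If one of the sites should fall short of qualified children, more children could be covered at one of the other sites", and Methodology says "In the unlikely event that one site might have difficulty with subject recruitment, additional children will be enrolled at another study site". Methodology also excludes the data of a child whose parent cannot learn to deliver the training safely.

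For PDMS-2, GMFM and the two walk tests, Data Analysis states: "A one-way analysis of variance (ANOVA) with repeated measures will be used for comparison of treatment groups for parametric dependent variables". PEDI and FMS are assigned to a Friedman test, and for StepWatch "StepWatch data will be examined with the Wilcoxon sign rank test for paired data". No site factor, stratification or covariate appears there or in Power Analysis.

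**The concern.** A factor used to restrict the randomisation normally appears in the analysis. Here site is the stratum, and it also tracks population and the person who coaches the family. When arms are balanced within site, site differences drop out of the difference between arm means. If the model ignores site, the same differences remain in the residual variance. The standard error is then too large for the design and power is lost.

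A second question arises when the balance fails. If a site stops early and its places are filled elsewhere, or if data are excluded, the arms may be unequal within a site, and the unadjusted arm difference then contains part of the site difference. With 24 children in total, both effects deserve a calculation.

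**Working it through.** **Inputs from the documents.** 12 per arm, 4:4 at three sites (Enrollment procedures); alpha 0.05 (Data Analysis), taken as two-sided because sidedness is not stated; effect size 1.87, power 0.95, N = 18 for PDMS-2 Locomotion change (Power Analysis, Fig. 4 caption); 80% power at 12 per group for 3000 strides/day (Power Analysis).

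**Assumed.** The site share of between-child variance, rho, is not in the documents; 0 to 0.4 is used. Site effects are fixed and equally spaced.

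**1. The plan's own figure.** A two-sample t-test with d = 1.87 has power 0.935 at 8 per arm and 0.961 at 9 per arm. So 9 per arm is the smallest size reaching 95%, and N = 18 reproduces. The StepWatch statement gives no SD; 80% power at 12 per arm implies d = 1.197, an SD of about 3000/1.197 = 2,506 strides/day. I use d = 1.197 only as a benchmark for an effect with 80% power.

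**2. Standard error without site.** Let s² be the within-site variance and V the variance of the site effects, so V/s² = rho/(1 − rho). Eight children per site put 8 × 3 × V = 24V into the residual sum of squares on 22 df. The ratio of the reported to the correct standard error is about √(1 + (24/22) × rho/(1 − rho)):
- rho 0.1: √(1 + 1.091 × 0.111) = 1.06
- rho 0.2: √(1 + 1.091 × 0.250) = 1.13
- rho 0.3: √(1 + 1.091 × 0.429) = 1.21

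**3. Power and type I error with 4:4 intact.** Simulation, 100,000 runs per setting, one outcome or change score per child, effect in within-site SD units. Without site the test has 22 df; with an additive site term, 20 df.

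| rho | Type I error, no site | d = 1.197: no site → site | d = 1.87: no site → site |
|---|---|---|---|
| 0 | 4.9% | 79.9% → 79.5% | 99.2% → 99.2% |
| 0.1 | 3.9% | 76.5% → 79.7% | 98.9% → 99.2% |
| 0.2 | 2.9% | 71.9% → 79.5% | 98.4% → 99.2% |
| 0.3 | 2.0% | 66.2% → 79.5% | 97.5% → 99.1% |
| 0.4 | 1.1% | 59.0% → 79.9% | 96.1% → 99.2% |

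With the site term, type I error stays at about 5%. If d = 1.197 is read in total-SD units instead, the gains at 10%, 20% and 30% are about 3, 6 and 8 points.

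**4. When 4:4 fails.** From a hat with four slips of each kind, a site stopping after 5 draws is always unbalanced. After 6 draws, P(3:3) = C(4,3) × C(4,3)/C(8,6) = 16/28, so P(4:2 in either direction) = 12/28 = 43%. Suppose (my assumption) the two undrawn slips go to a second site. With site means a and b and a 4:2 split at the first site, the arm contrast shifts by (4a + 4b)/12 − (2a + 6b)/12 = (a − b)/6. If these are the two most different sites, that is 0.14, 0.20 or 0.27 within-site SD at rho 0.1, 0.2 or 0.3. In simulation, the unadjusted type I error within those splits was between about 4.5% and 5%; over all splits at six draws it was about 4%, 4% and 3%.

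**The case against.** Several points against the concern stand.

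- The 80%-power benchmark comes from the StepWatch statement, and StepWatch is not analysed by the ANOVA. The only effect size given for an ANOVA outcome is 1.87, where omitting site costs almost nothing. A reader might infer that the trial is underpowered for PDMS-2; the plan's figures do not support that.
- The calculation uses one value per child, while the plan has four visits and was powered on change scores. Stable differences in level between sites cancel in change or arm-by-time comparisons. The population contrasts in Study Sites suggest level differences at least as much as differences in change.
- Operator differences are reduced by the joint two-day training, the common speed criterion and, for GMFM and PDMS-2, blinded video scoring. These do not remove differences in population or in delivery.
- A reader might infer that the shortfall rule biases the result systematically. It does not: assignment is still by random draw, so the imbalance is a matter of chance, and the check above showed no excess of false positives. The 43% also applies only to a site stopping at exactly six.
- A site term is not free everywhere. The walk tests are done only in children able to walk with a device, and all children start pre-ambulatory. With 4 per arm (illustrative) and d = 1.87, going from 6 to 4 df cuts power from 60% to 52% if sites do not differ.
- The rank tests now named are within-subject tests, so there is no between-arm rank test to stratify yet.

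What survives is that the model omits a factor the draw was balanced on, and that including it costs very little for outcomes measured in all children.

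**Conclusion.** The concern holds as a minor efficiency point. While 4:4 holds, leaving site out makes the arm test conservative; it neither biases the arm contrast nor inflates type I error, so it does not threaten a positive result. The cost in power ranges from nil, if sites do not differ in the analysed quantity, to about 13 points at an effect with 80% power and an assumed 30% site share. It is small throughout at the planned PDMS-2 effect. No effect size is given for GMFM, PEDI, FMS or the walk tests, so the loss for those cannot be placed within this range. If balance within sites is lost, the realised unadjusted difference carries part of any site difference, and a site term would remove it. All sizes rest on site shares that I assumed and on one analysed value per child.

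**What to change.** In Data Analysis, state that the between-arm models for PDMS-2 and GMFM include site (three levels) as a fixed factor, and that any between-arm model adopted for StepWatch, PEDI or FMS does the same. If a two-sample rank test replaces the within-subject tests now named, stratify it by site. For the 10-meter and 1-minute walk tests, include site only if enough children contribute data in each site-by-arm cell, with the threshold set in advance.

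The cost is a sentence or two and 2 of 22 error degrees of freedom. With all 24 children and no site differences that is about 0.4 point of power (79.9% to 79.5%); it is more if few children are analysed. No new data are needed.

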Outcome measures at the *activity level* of the International Classification of Functioning, Disability and Health (ICF) Model will include the Gross Motor Function Measure (GMFM), Peabody Developmental Motor Scales-2 (PDMS-2), Functional Mobility Scale (FMS), the Timed 10-meter Walk Test, the 1-minute Walk Test and the StepWatch accelerometer. Outcome measures at the *participation level* of the ICF Model will be the Pediatric Evaluation of Disability Inventory Caregiver Mobility Scale (PEDI). Videotapes of assessments will be scored by an assessor blinded to group allocation for the GMFM and PDMS-2. StepWatch data will be collected for all awake daytime hours over a 7 day period at study onset before treadmill training commences and at each of the post-intervention assessments. The StepWatch monitor will be secured around the child's ankle with a small knit cuff. [name] has successfully employed this method of monitor attachment in toddlers with and without motor limitations.^{23,36} StepWatch outcomes will be average number of strides/day and the percentage of the time walking.

[figure not shown]
In order to address specific aim # 1 (optimal parameters for dosing home-based treadmill training by comparing high-intensity to low-intensity treadmill training) and specific aim # 2 (effects of high- versus low-intensity treadmill training on walking attainment and overall walking activity), between-group differences of all the outcome measures will be analyzed as described in the next section. Specifically, between-group differences in GMFM and PDMS-2 will examine the effects of dosage on walking attainment and skills related to standing and walking. The changes in support needed for walking will be measured by the FMS in the two groups. Differences in walking speed and walking endurance will be analyzed using the data from the Timed 10-meter Walk Test and the 1-minute Walk Test, respectively. The parent perspective on overall child mobility will be analyzed by using the PEDI. Finally, overall walking activity will be shown by between-group differences from the StepWatch data.

Data Analysis

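### StepWatch is powered on a difference between the two intensity groups but is given only a within-child paired test; PEDI and FMS carry a lesser fault of the same kind

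*Combined protocol and SAP*

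**What the plan says.** The design is two parallel arms. Enrollment procedures states that "twelve children will receive high-intensity treadmill training and twelve children will receive low-intensity treadmill training". Methodology adds that "Group allocation will be determined by blinded drawing from a hat", with four children per arm at each of three sites unless a site falls short. Nothing pairs a child in one arm with a child in the other.

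The end of Methodology ties both specific aims to group comparisons: "between-group differences of all the outcome measures will be analyzed as described in the next section". For StepWatch it says that "overall walking activity will be shown by between-group differences from the StepWatch data". The same section defines two StepWatch outcomes, the mean daily stride count and the share of time spent walking.

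Power Analysis claims, for 12 children per group, "80% power to detect a 3000 stride/day difference in treatment intensity as measured with the StepWatch monitor". The basis is "cross-sectional StepWatch average stride/day data from 17 youth with CP ages 2-3 years".

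Data Analysis then gives three rules:
- PDMS-2, GMFM and the two timed walk tests get a repeated-measures ANOVA, described as comparing the treatment groups.
- For PEDI and FMS, analysis "will be conducted using the Friedman test for comparison between groups".
- For StepWatch, "StepWatch data will be examined with the Wilcoxon sign rank test for paired data".

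A further sentence allows post hoc tests where suitable, without naming any. Alpha is 0.05.

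**The concern.** The question is whether the more intensive schedule produces more walking than the less intensive one. Both arms train on the treadmill and both keep their usual physical therapy (Interventions), and the children are enrolled because they show signs of being ready to walk. Improvement common to both arms is therefore plausible, and it is what a paired test picks up.

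An analyst who followed the StepWatch sentence would have two ways to run it. Pooled over arms, the result says nothing about dose. Run in each arm separately, it invites the reading that dose matters if one arm reaches significance and the other does not, which is not a test of the difference. Either way, the part of aim 2 that concerns overall walking activity would be reported without a valid test.

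**Working it through.** **1. The plan's own figure.** The stated StepWatch power is 80% for 3,000 strides/day with 12 per arm. No SD and no test are given, so it cannot be reproduced; one can only solve for the SD it implies. A two-sided two-sample t-test with 12 per arm reaches 80% at a standardised difference of 1.197, so SD = 3,000 / 1.197, about 2,507 strides/day. Other conventions imply 2,623 (two-sided, normal approximation) or 2,863 (one-sided t). Each of these is a calculation for two independent groups, not for paired data.

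**2. What each test uses.** Let D be a child's change from baseline to a chosen visit.
- Signed-rank: W = sum of the ranks of |D| over children with D > 0. Group membership does not enter. If a gain g is added to every child, W rises.
- Rank-sum on change: U = number of high/low pairs with D(high) > D(low). A shared gain g cancels, because (D(high) + g) − (D(low) + g) = D(high) − D(low).
- Friedman, with the child as block and the four visits as conditions: values are ranked within each child, and group again does not enter. It could compare arms only if the arms were conditions within matched blocks, and no such blocks are described.

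**3. Size when there is no dose effect.** Assumptions: normal changes, 12 per arm, two-sided 0.05, shared gain in units of the SD of change. The gains are assumed because the plan gives no change or SD.

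| Shared gain | 0.2 SD | 0.5 SD | 0.8 SD |
|---|---|---|---|
| Signed-rank, arms pooled: rejects | 15% | 63% | 95–96% |
| Signed-rank per arm: only the high-intensity arm gains significantly | 7% | 22% | 22% |
| Rank-sum on change: rejects | about 4.5% | about 4.5% | about 4.5% |

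The middle row can be checked. Exactly one arm, either one, is significant in 15.3%, 43.2% and 44.4% of trials. Half of these are 7.7%, 21.6% and 22.2%, and counting only significant gains takes the first to about 7%.

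**4. The same point in strides.** Take SD 2,507 at each visit and within-child correlation 0.5 (both assumed), so that the SD of change = 2,507 × √(2 × (1 − 0.5)) = 2,507. If both arms gain 3,000, the pooled signed-rank test rejects in 100% of trials and rank-sum in 4.6%. If the arms gain 5,000 and 2,000, a true difference of 3,000, the pooled signed-rank test again rejects in 100% and rank-sum in 76%. The paired test gives the same answer with and without a dose effect.

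**5. Power after the change.** If 2,507 is the SD of change, rank-sum has about 76–77% where the t-test has 80%. The SD governs this: the t-test has 94%, 80%, 65%, 52% and 42% at SD 2,000, 2,500, 3,000, 3,500 and 4,000.

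**The case against.** The strongest reply is that the StepWatch sentence is a slip: the two Wilcoxon tests are easily confused, the intended contrast is plain from Methodology, and a statistician is to perform the analysis. That may be so, but the sentence expressly adds that the data are paired, and a slip needs the same correction. The allowance for post hoc tests does not help, since it names no test, contrast or visit. Balanced allocation within site does not help either, because it does not pair children.

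Some of the reply stands. The total of 24 comes from the PDMS-2 calculation (18 plus 6); StepWatch is then given a power at that size, and no single primary outcome is named. So the fault does not undo the sample size.

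A reader might also infer more than the documents support:
- *That no outcome has a between-group analysis.* The ANOVA sentence states that it compares treatment groups. Its label is loose and needs only clarifying.
- *That PEDI and FMS are as badly served as StepWatch.* Their sentence states the right contrast and names the wrong procedure.
- *That separate tests per arm would falsely favour high intensity in 43–44% of trials.* That figure counts either arm; the relevant pattern is about 22%.
- *That the pooled test would usually miss a real dose effect.* The very low rejection rates, such as 2.1% when the arms change by +1,500 and −1,500 strides, require the low-intensity arm to decline, which fits poorly with shared improvement.
- *That the correction cuts power to 62%.* That needs 2,507 to be a single-visit SD, a visit correlation of 0.3, and equal SDs at both visits. These children do not yet walk at baseline, so early stride counts may be near the floor. If the baseline SD were half the follow-up SD, power would be 78%, 87% and 95% at correlations 0.3, 0.5 and 0.7.

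**Conclusion.** The concern holds for StepWatch and must be corrected before analysis. The test named does not address the comparison that Methodology promises and Power Analysis relies on. This follows from the form of the test and from the two unmatched arms, and needs no numerical assumption. The rejection rates only show how far the result could mislead; they rest on normal data and assumed gains.

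For PEDI and FMS the finding is narrower: a wrong procedure attached to a correctly stated contrast. No rate is put on it here, because FMS is a rating from 1 to 6, ties are likely, and a calculation on continuous normal data would not transfer well.

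The documents do not show that the stated 80% is wrong. It cannot be checked without an SD.

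**What to change.** Replace the PEDI/FMS sentence and the StepWatch sentence in Data Analysis with wording such as:

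> *StepWatch strides/day and percentage of time walking, PEDI and FMS will each be compared between the high- and low-intensity groups with a two-sided Wilcoxon rank-sum test on change from baseline to [one stated visit], stratified by site if feasible.*

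Both StepWatch outcomes must be listed, or the second is left with no analysis. One visit must be stated, because there are three after baseline. A baseline-adjusted rank analysis (rank of follow-up regressed on group and rank of baseline) is an acceptable alternative.

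Keep the signed-rank and Friedman tests only to describe change within each arm. In the ANOVA sentence, add that group is the between-child factor and that group-by-time is the test of interest.

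The cost is a few sentences, with no new data, visits or children, and possibly a few points of power: about 76–77% in place of 80% under the t-test reading with an SD of change of 2,507. The sponsor should state the SD and the test behind the 80%, so that this can be confirmed.
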